### **6.9 Concomitant Medications/Medical Care**

All medications taken or medical procedures performed within 12 weeks prior to Day 0 and during the study must be recorded on the case report forms (CRFs).

### **6.10 Permitted Supportive Therapy**

Anti-emetics, anti-diarrheals, analgesics, nutritional and fluid supplementation, and packed red blood cell transfusions are permitted as supportive therapy during the study. All medications and interventions must be recorded as concomitant medications in the CRFs.

### **6.11 HLA Testing**

A blood sample will be collected at the Day 0 visit and sent to a central laboratory for HLA typing. If the subject has a record of previous high resolution HLA testing and access to the results, this HLA testing is not required.

### **6.12 Downloading of EP data from CELLECTRA®-5P device**

Within 48 hours following each treatment with INO-3112, data should be downloaded from the EP device and the data file that is created should be sent to the Sponsor or designee by email to [[contact]](mailto:[contact]). Instructions on how to download the data are provided in Appendix 7. Training will be provided.

### **6.13 Restrictions**

Subjects should not be vaccinated (e.g. influenza vaccine) within 2 weeks of (before or after) any dose of INO-3112.

Subjects should not receive a course of systemic corticosteroids ( $\geq 2$  mg/kg of prednisone or equivalent for 5 days) within 2 weeks before or after any dose of INO-3112.

---

## 7 EVALUATION OF SAFETY AND MANAGEMENT OF TOXICITY

### 7.1 Safety Parameters

The safety of the INO-3112 DNA plasmid vaccines will be measured and graded in accordance with the document entitled “Common Terminology Criteria for Adverse Events (CTCAE)”, version 4.03 issued by the US Department of Health and Human Services on June 14, 2010 (Appendix 4).

#### 7.1.1 Adverse Events (AEs)

An adverse event (AE) is defined as any unfavorable and unintended change in the structure, function, or chemistry of the body, or worsening of a pre-existing condition, temporally associated with the use of a product whether or not considered related to the use of the product. In this study, such changes will be monitored, classified, and summarized, and as Clinical or Laboratory AEs, respectively. Medical condition/diseases present before starting the investigational drug will be considered adverse events only if they worsen after starting study treatment.

An unexpected AE is one not identified in the Clinical Investigator’s Brochure (CIB) or otherwise not expected from the characteristics of the clinical material. AEs include the following:

- Pre- or post-treatment complications that occur as a result of protocol mandated procedure during or after the first screening visit (before the administration of study drug)
- Any pre-existing condition that increases in severity, or changes in nature during or as a consequence of the study drug phase of a human clinical trial, will also be considered an AE
- Complications and termination of pregnancy; see Section 7.4 for additional information
- All AEs that occur from the study screening visits onwards and throughout the duration of the study, including the follow-up off study treatment period should be recorded as an AE

AEs do not include the following:

- Medical or surgical procedures (e.g., surgery, endoscopy, tooth extraction, transfusion) performed; the condition that leads to the procedure is an AE
- Pre-existing diseases or conditions or laboratory abnormalities present or detected before the screening visits that do not worsen
- Situations where an untoward medical occurrence has not occurred (e.g., hospitalization for elective surgery, social and/or convenience admissions).
- Overdose without clinical sequelae

- 
- Any medical condition or clinically significant laboratory abnormality with an onset date before the consent form is signed and not related to a protocol associated procedure is not an AE. It is considered to be pre-existing and should be documented on the medical history CRF
  - Uncomplicated pregnancy (documented on a pregnancy CRF)
  - An induced elective abortion to terminate a pregnancy without medical reason (documented on a pregnancy CRF)

### 7.1.2 Serious Adverse Events (SAEs)

A serious adverse event (SAE) is any AE that meets one of the following conditions:

- Death during the period of surveillance defined by the protocol;
- Is immediately life-threatening (e.g., subject was, in the view of the Investigator, at immediate risk of death from the event as it occurred). This does not include an AE that, had it occurred in a more serious form, might have caused death;
- An event requiring inpatient hospitalization or prolongation of existing hospitalization during the period of protocol defined surveillance (including any overnight stay in the hospital, regardless of the length of stay, even if the hospitalization is only a precautionary measure to allow continued observation. However, hospitalization (including hospitalization for an elective procedure) for a pre-existing condition that has not worsened, does not constitute an SAE;
- Results in congenital anomaly or birth defect;
- Results in persistent or significant disability/incapacity or substantial disruption of the ability to conduct normal life functions;
- Is an important medical event that may not result in death, be life threatening, or require hospitalization, but based upon appropriate medical judgment, may jeopardize the subject and may require medical or surgical intervention to prevent one of the outcomes listed above. Examples of such medical events include allergic bronchospasm requiring intensive treatment in an emergency room or at home, blood dyscrasias or convulsions that do not result in inpatient hospitalization, or the development of drug dependency or drug abuse;
- Is medically significant or requires intervention to prevent one or other of the outcomes listed above. Examples of “other medically significant events” are:
  - Intensive treatment in an emergency room or at home for allergic bronchospasm
  - Blood dyscrasias or convulsions that do not result in hospitalization
  - Development of drug dependency or drug abuse

- Development of malignancies

#### Clarification of Serious Adverse Events

- Death is an outcome of an AE, and not an adverse event in itself
- The subject may not have been on investigational medicinal product at the occurrence of the event. Dosing may have been given as treatment cycles or interrupted temporarily before the onset of the SAE, but may have contributed to the event
- “Life-threatening” means that the subject was at immediate risk of death from the event as it occurred. This does not include an event that might have led to death if it had occurred with greater severity
- Complications that occur during hospitalizations are AEs. If a complication prolongs the hospitalization, it is an SAE
- Inpatient hospitalization means the subject has been formally admitted to a hospital for medical reasons, for any length of time. This may or may not be overnight. It does not include presentation and care within an emergency department

The investigator should attempt to establish a diagnosis of the event on the basis of signs, symptoms, and/or other clinical information. In such cases, the diagnosis should be documented as the AE and/or SAE and not the individual signs/symptoms.

Serious adverse events that are ongoing should be followed until resolution. The reporting period for SAEs is described in Section 9.3.2.

#### **7.1.3 Severity Codes for AEs**

Study personnel will grade laboratory AEs and clinical AEs (based on discussions with study participants) with respect to the following levels of severity as defined in Common Terminology Criteria for adverse events (CTCAE) of the National Cancer Institute for reporting of all serious adverse events (SAE) or the Acute Radiation Morbidity Scoring Criteria (RTOG).

- Mild (Grade 1);
- Moderate (Grade 2)
- Severe (Grade 3);
- Potentially Life Threatening (Grade 4)
- Death (Grade 5)

A copy of the CTCAE version 4.03 is provided in Appendix 4 and may be downloaded from the CTEP home page (<http://ctep.cancer.gov/reporting/ctc.html>):

A copy of the Acute Radiation Morbidity Scoring Criteria can be downloaded from the Radiation Oncology Therapy Group home page (<http://www.rtog.org/ResearchAssociates/AdverseEventReporting/AcuteRadiationMorbidityScoringCriteria.aspx>).

## 7.2 Causal Relationship of Clinical Material to AEs

A causally related AE is one judged to have a possible, probable or definite relationship to the administration of the clinical material (INO-3112). An AE may also be assessed as not related to the investigational product. The Investigator is responsible for reporting adverse events and judging the relationship between the administration of the clinical material and a subsequent AE because the investigator is knowledgeable about the subject (e.g., medical history, concomitant medications), administers the investigational product, and monitors the subject's response to the investigational product. The Investigator is aware of the subject's clinical state and thus may be sensitive to distinctions between events due to the underlying disease process versus events that may be product related and may have observed the event. The Sponsor will assess the overall safety of the investigational product and determine whether to report expeditiously to the FDA.

The following guidance should also be taken into consideration:

- Temporal relationship of event onset to the initiation of study drug;
- Course of the event, considering especially the effects of dose reduction, discontinuation of study drug, or reintroduction of study drug (where applicable);
- Known association of the event with the study drug or with similar treatments;
- Known association of the event with the disease under study;
- Presence of risk factors in the Study Subject or use of concomitant medications known to increase the occurrence of the event;
- Presence of non-treatment-related factors that are known to be associated with the occurrence of the event

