Based on clinical experience with INO-3112 from similar protocols using electroporation-mediated drug delivery and the overall safety database encompassing all studies of Inovio DNA delivered by electroporation with CELLECTRA®-5P, we do not expect to observe any severe or dose-limiting side

---

effects or toxicities. Side effects of vaccination with INO-3112 may include discomfort related to the electroporation technique, such as transient local edema, swelling, or pain.

In the phase I studies of VGX-3100 delivered by EP in women with a history of treated CIN 2/3 there were no serious adverse events attributed to treatment in any of the subjects enrolled and no participants discontinued early.

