### **2.2 Primary Objective**

Evaluate the safety and tolerability of immunotherapy with INO-3112 when delivered IM followed by EP with CELLECTRA®-5P in women with newly diagnosed, inoperable cervical cancer associated with HPV-16 and/or HPV-18 after completion of standard chemoradiation therapy with curative intent (Cohort 1) or in women with persistent and/or recurrent cervical cancer associated with HPV-16 and/or HPV-18 following salvage therapy (Cohort 2) compared to that expected/reported with “standard” therapy alone.

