### **Primary Safety Endpoints:**

1. Incidence of adverse events (all, severe [graded per CTCAE v4.03], unexpected, serious) classified by system organ class (SOC), preferred term, severity, and relationship to study medication and schedule
2. Injection site reactions including pain, tenderness, erythema and induration at administration site
3. Rates of acute gastrointestinal, genitourinary, or other chemoradiation side effects above the expected, graded per Acute Radiation Morbidity Scoring Criteria (RTOG)
4. Changes in laboratory parameters from baseline

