### 7.5.2 Events Requiring Expedited Reporting

Events requiring expedited reporting (ERER) will be defined as treatment- or EP-related adverse events including any of the following:

- Grade 3 or greater injection site pain, tenderness, erythema, and/or induration recorded  $\geq 1$  hour after study treatment (see Table 6.1)
- Grade 3 or greater fever assessed by the Principal Investigator as possibly, probably or definitely related to study treatment
- Grade 3 or greater systemic symptoms assessed by the Principal Investigator as possibly, probably or definitely related to study treatment

as defined in the “Common Terminology Criteria for Adverse Events (CTCAE)”, version 4.03 issued by the US Department of Health and Human Services on June 14, 2010 (Appendix 4). The worse grade for that particular event is to be documented on the CRFs.

Sites should inform the Sponsor of any ERER within 72 hours to discuss whether further dosing should continue for that participant.

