### 7.5.3 Stopping Rules (Criteria for Pausing of Study)

- 7.5.3.1 If at any time during the study one third (1/3) or more subjects experience an ERER assessed as possibly, probably or definitely related to study treatment, further enrollment and study treatments will be halted immediately until a thorough investigation has been conducted by the Medical Monitor and Principal Investigator.
- 7.5.3.2 After any SAE, potentially life threatening AE or death assessed as possibly, probably or definitely related to study treatment, further enrollment and study treatments will be halted immediately until a thorough investigation has been conducted by the Medical Monitor, Principal Investigator and IRB (if applicable).
- 7.5.3.3 If three or more subjects in this study, experience the same grade 3 or 4 adverse event, assessed as possibly, probably or definitely related to study treatment, further enrollment and study treatments will be halted immediately until a thorough investigation has been conducted by the Medical Monitor and Principal Investigator.
- 7.5.3.4 In the event of any unexpected Grade 4 toxicities, assessed as possibly, probably or definitely related to study treatment, further enrollment and study treatments will be halted immediately until a thorough investigation has been conducted by the Medical Monitor, Principal Investigator and IRB (if applicable).

- 7.5.3.5 The study will be halted for any report of Grade 3 anaphylaxis from immunotherapy/EP with INO-3112 in two or more patients (as graded per “Common Terminology Criteria for Adverse Events (CTCAE)”, version 4.03 issued by the US Department of Health and Human Services on June 14, 2010 (Appendix 4)).

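### Causality is judged against INO-3112 and never names electroporation or the device, so EP-caused events outside the injection site may be rated unrelated

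*Combined protocol and SAP*

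**What the plan says.** The primary objective (section 2.2) is to "Evaluate the safety and tolerability of immunotherapy with INO-3112 when delivered IM followed by EP with CELLECTRA"-5P. The regimen under test is therefore product plus electroporation. Section 1.4.3 names among the possible side effects "discomfort related to the electroporation technique, such as transient local edema, swelling, or pain".

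Section 7.2 contains the only definition of causality: "A causally related AE is one judged to have a possible, probable or definite relationship to the administration of the clinical material (INO-3112". It adds that "An AE may also be assessed as not related to the investigational product", and its list of considerations refers to the study drug. EP and the device do not appear in it.

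Primary endpoint 1 (section 3 and synopsis) classifies adverse events by "severity, and relationship to study medication and schedule". Primary endpoint 2 counts injection-site reactions with no causality condition. Section 8.2 tabulates events by type and grade.

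Section 7.5.2 opens with "Events requiring expedited reporting (ERER) will be defined as treatment- or EP-related adverse events", but its fever and systemic-symptom bullets ask about relation to study treatment. The pausing rules 7.5.3.1 to 7.5.3.4 use the same term; 7.5.3.3, for example, concerns three or more subjects who "experience the same grade 3 or 4 adverse event, assessed as possibly, probably or definitely related to study treatment".

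**The concern.** The objective and the causality definition have different scopes. An investigator who takes 7.2 at its word and thinks an event came from the current, and not from the plasmid, has grounds to mark it not related. Section 9.4 does not close the gap: it sends device problems through complaint reporting and assigns no causality to an adverse event.

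Two things are at stake. First, the relationship classification in endpoint 1 could understate what the regimen does to patients. Attribution between product and device would also be hard to recover later if it was never recorded. Second, the reporting and pausing sections vary in wording, so two sites could treat the same EP-caused event differently.

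**Working it through.** The plan gives no figure on this point, so the check is a comparison of wording.

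| Section | Relatedness is judged against | EP or device named? |
|---|---|---|
| 7.2, definition | administration of INO-3112 | no |
| 7.2, not-related option | investigational product | no |
| 3, primary endpoint 1 | study medication | no |
| 7.2.2 and 9.3.2, events learned of later | study treatment | no |
| 7.5.2, stem | treatment or EP | yes |
| 7.5.2, injection-site bullet | no test beyond the stem | through the stem |
| 7.5.2, fever and systemic bullets | study treatment | not in the bullets |
| 7.5.3.1 to 7.5.3.4 | study treatment | no |
| 7.5.1 and 7.5.3.5, anaphylaxis | study treatment/EP, immunotherapy/EP | yes |
| 4.4, Grade 3 and Grade 4 toxicity | study treatment/EP | yes |

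**Step 1: does 7.2 cover EP?** Section 5.1 defines an investigational product as a pharmaceutical form of an active ingredient, and section 5.8 accounts for the device separately. On those definitions, an event caused by the device alone fits the not-related option. On the other hand, 7.2 speaks of administration, and section 5.7 describes injection and electroporation as one procedure. Both readings are open.

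**Step 2: does *study treatment* include EP?** The usage is mixed. The 7.5.2 stem sets EP beside treatment as an alternative. Section 3, however, calls Day 0 both the first study treatment/EP and the initial study treatment. The reminder card in Appendix 9 describes redness, swelling and pain at the injection site as reactions to the study treatment. No section defines the term.

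**Step 3: follow one event.** Take a faint during the pulses. In Appendix 4, syncope and vasovagal reaction have no Grade 1 or 2 entry, so it is at least Grade 3.

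- All-event tables: counted under either reading.
- Endpoint 2: not counted, because it is not an injection-site reaction.
- Endpoint 1, relationship: related or not related, depending on how 7.2 is read.
- Section 7.5.2: the stem includes it as EP-related; the systemic-symptom bullet asks about study treatment.
- Rule 7.5.3.3: counts or not, depending on what study treatment means.

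**Step 4: how sensitive are the counts?** Section 8.1 plans n = 10. One subject moved between related and not related changes the proportion by 1/10, or 10 percentage points. Rules 7.5.3.2 and 7.5.3.4 need one event and 7.5.3.3 needs three subjects. Rule 7.5.3.1 needs 4 of 10, since 10/3 = 3.33. These counts are small enough for a few classifications to matter. The documents give no rate for severe events due to EP alone, so no probability follows.

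**The case against.** The strongest reply is that the protocol, read as a whole, already covers EP. Administration means injection followed at once by EP, and the threshold for related is only *possible*. An investigator could seldom rule out a possible link to an injection given at the same site immediately beforehand. Study treatment and study treatment/EP are used interchangeably. The 7.5.2 stem, 7.5.1, 7.5.3.5 and 4.4 name EP. Adverse events on study are reported whatever their cause (7.2.2), and serious ones without regard to causality (9.3.2). Injection-site effects, the ones the protocol expects, carry no causality filter in endpoint 2.

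Much of this stands, and it rules out two stronger readings.

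- A reader might infer that EP-caused events drop out of the safety tables and the halting rules. The documents do not support that. Section 8.2 plans no related-only table, the events remain in the all-event tables, and several of the safety rules name EP. Even where only study treatment appears, the term may include EP.
- A reader might infer a sizeable undercount, for example from the painfulness of EP in earlier studies (mean VAS 6.2 immediately afterwards in HPV-001, section 1.3.1). Injection-site pain is already counted without a causality test, and Table 6.1 does not grade by VAS. Section 1.3.1 also reports very few related Grade 3 events, and no related Grade 4 or serious events, after 551 doses of VGX-3100 in 185 subjects.

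The reply does not remove the gap in 7.2 or the difference between the 7.5.2 stem and two of its bullets. The anaphylaxis rules name EP for that one event only, and 4.4 governs the individual subject, not the study.

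**Conclusion.** The point holds as an ambiguity, not as an express exclusion. The only causality definition is narrower in its wording than the primary objective. For EP-caused events outside the injection site, the relationship classification in endpoint 1 could understate the regimen's toxicity if sites apply 7.2 literally. The relatedness wording in the safety sections is inconsistent and must be reconciled.

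No magnitude is claimed. The effect depends on how often such events occur and how sites read 7.2, and the documents settle neither. The CRF is not among the documents, so it may already separate product from device. This is a cheap improvement, worth making because the attribution is hard to reconstruct afterwards.

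**What to change.** - In 7.2 and primary endpoint 1, define a related event as one with a possible, probable or definite relationship to INO-3112 and/or the injection/EP procedure or device.
- On the CRF, record relationship to the product and relationship to EP/device as separate items, if it does not already do so.
- In 8.2, tabulate related events for product, for EP/device, and for either, beside the all-event tables.
- The sponsor should reconcile 4.4, 7.2.2, 7.5.2, 7.5.3 and 9.3.2 on whether study treatment includes EP. Which halting rule is right is not for this review to say.

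The cost is some wording, at most one more CRF item and a few table columns. The downside is that slightly more events will be counted as related.

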### 7.2.1 Abnormal Laboratory Value

Laboratory abnormalities are usually not recorded as AEs or SAEs. However, laboratory abnormalities (e.g., serum chemistry, hematology, CPK, urinalysis) independent of the underlying medical condition that require medical or surgical intervention or lead to study treatment interruption or discontinuation must be recorded as an AE, as well as an SAE, if applicable. In addition, laboratory or other abnormal assessments (e.g., electrocardiogram, x-rays, vital signs) that are associated with signs and/or symptoms must be recorded as an AE or SAE if they meet the definition of an AE (or SAE) as described in Sections 7.1.1 and 7.1.2. If the laboratory abnormality is part of a syndrome, record the syndrome or diagnosis (e.g., anemia) not the laboratory result (e.g., decreased hemoglobin).

Any laboratory abnormality that is new in onset or worsened in severity or frequency from the baseline condition and meets one of the following criteria will be recorded as an AE:

- Requires therapeutic intervention or diagnostic tests
- Leads to discontinuation of study treatment
- Has accompanying or inducing symptoms or signs

- Is judged by the investigator as clinically significant

Grade is an essential element of these criteria. Each CTCAE grading term in the current version is a unique representation of a specific event used for medical documentation and scientific analysis and is a single MedDRA Lowest Level Term (LLT).

Investigators are asked to take the CTCAE grading criteria into account when assessing if a laboratory abnormality qualifies as a laboratory AE. Their clinical judgment ultimately determines whether the abnormality in question is “clinically significant (CS)” or “not clinically significant (NCS)” and the severity of the event. CTCAE grading can be used as a reference when making this determination. It is the responsibility of the Investigators to ensure all AEs are accurately reported and graded.

